## 13.0 STATISTICAL ANALYSIS

### 13.1 ANALYSIS OF PRIMARY OBJECTIVE

Total cost of care is defined as all stoma related costs accrued through the duration of the study period. Health care resource utilization data collected to support this objective includes treatments related to stoma and/or PSCs (topical medications, clinic visits, accessory use, etc.), social impact of stoma and/or PSCs (e.g. missed work/appointments), hospitalizations, ER visits, physician/clinic visits, ostomy-related medication use and therapies, and barrier utilization (not including pouch utilization). [REDACTED]

[REDACTED] A corresponding country specific unit cost or reasonable estimate (when data is not available) will be assigned to each of the health care resource units listed above. Total cost of care will be calculated by multiplying the units of health care resources by the corresponding country specific resource unit cost and then summing costs across the study period.

The primary objective will be analyzed via an analysis of covariance (ANCOVA) model comparing the mean daily total cost of care between the treatment ([REDACTED]) and control ([REDACTED]) arms. The model will be adjusted for the covariates listed in Section 12.4, site location, and relevant demographic variables. Formally, the null and alternative hypotheses being evaluated are:

- a) Null: No difference in the mean total cost of care for 12 weeks between [REDACTED] and control i.e.  $H_0: \mu_{Test} = \mu_{Control}$  vs.
- b) Alternative: The mean total cost of care for 12 weeks for [REDACTED] is not equal to that of the control i.e.  $H_A: \mu_{Test} \neq \mu_{Control}$ .

[REDACTED]

[REDACTED]

3. Given assumptions 1 and 2, this results in a difference in mean total cost of care for the [REDACTED] and control arms of [REDACTED].
4. Using Meisner's costs of PSC according to level of severity [REDACTED] for 50% of the population, the estimate of the standard deviation for total cost of care is [REDACTED]

Using the estimates above the sample size required for to achieve 80% power with a 2.5% type 1 ( $\alpha$ ) error would be 72 per arm completed for the primary endpoint and 93 completed per arm for the secondary endpoint. In order to cover both primary and secondary endpoints, an initial sample size of 93 completed per arm was chosen. Based on the findings of the first interim analysis with 92 subjects [REDACTED] the sample size has been increased to 105 subjects per arm.

### 13.5 INTERIM ANALYSIS

Given the uncertainty in the effect size estimates used to create the initial sample size requirement, this study employs an adaptive design. While the initial sample size was estimated based on available published data, the impact [REDACTED] will have in this population is not well known. Due to this limited knowledge, the data was analyzed once 92 subjects [REDACTED] were completed in each arm. Based on the interim findings it was determined that [REDACTED] and the sample size requires an increase to 105 subjects per arm to maintain 80% conditional power. [REDACTED]

[REDACTED] To allow for early stopping and a re-evaluation of sample size an additional interim analysis will be performed once 76( $\pm$ 5) subjects per arm have completed. The general approach of the adaptive design has been derived from Mehta and Pocock [6]. [REDACTED]

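### Could the first interim look have come at 92 completers per arm when a later look is planned at 71 to 81 per arm?

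*Combined protocol and SAP*

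**What the plan says.** The size of the first interim look appears twice.

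- The sample size paragraph under Section 13.1 gives the initial requirement: the number needed "would be 72 per arm completed for the primary endpoint and 93 completed per arm for the secondary endpoint", so that "an initial sample size of 93 completed per arm was chosen". It then reports the adaptation: "Based on the findings of the first interim analysis with 92 subjects [REDACTED] the sample size has been increased to 105 subjects per arm". No unit, total or per arm, is visible for the 92.
- Section 13.5 describes the same look in the past tense: "the data was analyzed once 92 subjects [REDACTED] were completed in each arm". It reports that "the sample size requires an increase to 105 subjects per arm to maintain 80% conditional power". In the future tense it adds that "an additional interim analysis will be performed once 76( $\pm$ 5) subjects per arm have completed", with early stopping and another sample size re-evaluation as the purpose.

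In both sections a redaction follows directly after the 92 subjects. In 13.5 it stands between that count and the verb.

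**The concern.** With the redaction skipped over, 13.5 puts the completed look at 92 per arm and the later look at no more than 81 per arm. An additional look cannot precede the first. Section 13.1 attaches no visible per-arm unit to the 92, although the other counts in the two sections (72, 93, 105, 76) are all per arm, so the two sections also seem to state the same fact differently.

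The first-look size is an input to conditional power and, in many adaptive designs, to boundaries or stage weights. Section 13.5 also governs a look that may stop the trial or change its size again. If 92 per arm had been entered for a look that held 46 per arm, those calculations would be wrong. A reader checking the adaptation from the public text could not tell which figure was used.

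**Working it through.** **Inputs.** From 13.1: initial size 93 per arm (186 in total), first look at 92 subjects, increased size 105 per arm (210 in total). From 13.5: next look at 76 ± 5 per arm, 80% conditional power. The planned sizes 72, 93 and 105 cannot be reproduced, because the cost difference, its standard deviation and the interim findings are blacked out. The check is therefore one of order and consistency.

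**Window of the coming look.** 76 − 5 = 71 and 76 + 5 = 81 per arm.

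**Reading A: 92 per arm.**
- Total at the first look: 2 × 92 = 184 of 186, or 98.9% of the initial plan, with 1 per arm left.
- The later look would fall 92 − 81 = 11 to 92 − 71 = 21 completers per arm before the first. This is impossible if both counts are on the same basis.

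**Reading B: 92 in total.** Equal allocation is assumed, since no ratio is visible.
- 92/2 = 46 per arm; 46/93 = 49.5% of the initial size and 46/105 = 43.8% of the increased size.
- To the second look: 71 − 46 = 25 to 81 − 46 = 35 more per arm. From there to 105: 105 − 81 = 24 to 105 − 71 = 34 more.
- Second look as a fraction of 105: 71/105 = 67.6% to 81/105 = 77.1%.
- Midpoint between the first look and the end: (46 + 105)/2 = 75.5, against the stated 76.

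Under B, the first look is at half of the initial plan and the second is about halfway through what then remained. Both are natural design choices.

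**Does the increase to 105 make sense under each reading?** As an illustration, assume conditional power under the current trend with a simple final test at critical value c:

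CP = Φ{ (z₁√n₁ − c√N)/√(N − n₁) + z₁√(N − n₁)/√n₁ }

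The interim z₁ that gives CP = 80% is:

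| n₁ per arm | c | N = 93 | N = 105 |
|---|---|---|---|
| 46 | 1.960 | 1.799 | 1.715 |
| 46 | 2.241 | 1.997 | 1.901 |
| 92 | 1.960 | 2.036 | 2.112 |
| 92 | 2.241 | 2.316 | 2.375 |

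With 46 per arm, a trend that gives 80% at 105 falls short of what 93 would need, so an increase is called for. With 92 per arm, a trend that gives 80% at 105 already exceeds what 93 would need, so no increase would have been required. Under these assumptions the sponsor's own decision also points to 46.

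**Are 13.1 and 13.5 shown to differ?** No. Each has hidden text in the same position, directly after the 92 subjects. The same qualifier, for example a per-arm count, could stand in both. In 13.5 such a count could be what the closing per-arm words refer to, and the sentence would then be correct.

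**The case for a change.** The best case for a change is that the per-arm words in 13.5 are visible and come after the redaction, so whatever is hidden, a reader of the public text sees 92 tied to each arm. The section governs a look with real consequences, and the repair would cost two sentences and one comparison with the interim report.

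Part of this stands. The visible sentence misleads if read straight through, and 92 per arm is not compatible with the rest of 13.5 when the counts are on the same basis. What does not stand is the step from there to a defect. Text that a sponsor has blacked out is not missing from the plan, and nothing shows that those who run or oversee the coming look rely on the redacted copy.

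A loss of power can be computed only by supposing stage weights and a two-stage final test that no visible text states, and by supposing that the analyst entered a figure contradicted by the data in hand. Such a number would describe an imagined mistake, and there is no sign of that mistake. The agreement of 46, 76 and 105 suggests the opposite, which also removes the reason to audit the interim calculation on this ground.

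**Conclusion.** The tension in the visible wording is real, but it is at most clerical, and correcting it would gain nothing for the trial. Read as a total, 92 gives 46 per arm, 49.5% of the initial 93, and looks in the order 46, 71 to 81, 105. Read as per arm, it puts the second look 11 to 21 completers per arm ahead of the first. Only the total reading works, and an informed analyst will adopt it.

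The first look is done; what remains to be carried out, the look at 76 ± 5 and the target of 105, is stated per arm without ambiguity. No error in the conditional power, the boundaries or the sample size is shown, and no planned number changes.

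This rests on equal allocation, on 76 and 92 counting the same kind of completer, and on the interim calculation having used the actual number of completers. The first two cannot be confirmed from the redacted text, but the figures agree with them. The third would be in doubt only if 92 per arm had been used, and nothing in the documents suggests that.

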## 14.0 FINAL REPORT

The Sponsor is responsible for issuing a final report to the study sites. It is the responsibility of the Investigator to provide a final report to the IRB/EC, as required.

### **15.0 MONITORING**

A qualified Hollister Incorporated monitor or designee(s) monitor(s) the study.

### **16.0 AMENDMENT PROCEDURES**

The sponsor is responsible for initiating any protocol amendments. Approval of the amendment must be obtained by the EC or IRB prior to implementation. Investigator(s) are notified of the changes, and a copy of the amendment is kept in the study file.

